6.16.2. Interim Analyses	
6.17. Annual Report Analyses	47
6.18. Clinical Trial Registry Analyses	47
7. References	48
8. Appendices	50

Table of Contents

Table		Page
Table AMBU.4.1.	Primary Objective and Endpoints	9
Table AMBU.4.2.	Secondary Objectives and Endpoints	9
Table AMBU.4.3.	Exploratory Objectives and Endpoints	12
Table AMBU.6.1.	Definition of Population	16
Table AMBU.6.2.	Weight/Treatment Dose Groups for Each Analysis Study Period and Population	16
Table AMBU.6.3.	Patient Characteristics (and Variables for Analysis)	20
Table AMBU.6.4.	Description and Derivation of Efficacy/Health Outcomes Measures and Endpoints	24
Table AMBU.6.5.	Description of Secondary Efficacy/Health Outcomes Analyses	33
Table AMBU.6.6.	Description of Exploratory Efficacy/Health Outcomes Analyses	36
Table AMBU.6.7.	Categorical Criteria for Abnormal Treatment-Emergent Blood Pressure and Pulse Measurement for Children by Age Group	41

P	ac	1e	5

Table of Contents

Figure		Page	
Figure AMBU.5.1.	Illustration of study design for clinical protocol I6T-MC-		
	AMBU	14	

I6T-MC-AMBU Statistical Analys	sis Plan Version 2
---------------------------------------	--------------------

I age t

Table of Contents

Appendix		Page
Appendix 1.	Oci Diary Calculations	51

3. Revision History

Statistical analysis plan (SAP) Version 1 was approved prior to the first patient visit on 19 December 2019.

Statistical analysis plan Version 2 was based on protocol amendment (c) approved 22 October 2021. The following updates were made in Version 2 of the SAP before the first interim analysis by the sponsor:

- Made the following changes to secondary endpoints:
 - Added additional estimand language for clarity.
 - o Updated definition of clinical remission based on protocol amendment.
 - o Updated wording for age group based on protocol.
 - Updated name of histologic-endoscopic mucosal remission to match protocol amendment.
- Made the following changes to exploratory endpoints:
 - o Removed as exploratory endpoints.
 - Updated wording of objectives to clarify exploratory nature of objectives/endpoints.
 - Added additional time points for summaries of Modified Mayo Score (MMS) subscores.
 - o Removed Urgency numeric rating scale (NRS) and Abdominal Pain NRS as they are already in the secondary endpoint table.
- Updated Study Schema Figure AMBU.5.1 according to protocol update.
- Updated population and treatment groups in Table AMBU.6.1 and Table AMBU.6.2 according to protocol update.
- Changed analysis approach for calculating confidence intervals in Section 6.1.3.
- Added language clarifying how missing data handling for continuous endpoints as well as modifications for missing data handling as part of the interim analysis (Section 6.3).
- Fixed categorical summary definitions for Bristol stool scale and at baseline in Table AMBU.6.3.
- Made the following changes to Table AMBU.6.4:
 - Updated definitions of MMS Clinical Remission, Alternate Clinical Remission, stool frequency (SF) component of clinical remission.
 - o Minor clarification of wording for Corticosteroid-free remission at Week 52
 - o For histology, added definitions for CCI , Histologic Remission, and histologic-endoscopic mucosal remission.
 - o For growth, added definitions for change from baseline (CFB) in height, CFB in weight, and height/weight z-scores and percentiles.
 - Removed definition of CCI
 - Added definition of EIM subcategory.
- Made the following changes to Table AMBU.6.5:

- Clarified missing data handling analysis methods for each endpoint variable (non-responder imputation [NRI], modified baseline observation carried forward (mBOCF), and as observed).
- Added the following secondary endpoints to be calculated: Pediatric Ulcerative Colitis Activity Index (PUCAI) CFB, Height CFB, Weight CFB, Histologic Remission, Histologic Improvement, and Histologic-Endoscopic Mucosal Remission, 30% improvement from baseline in Abdominal Pain.
- Clarified that Abdominal Pain will be summarized by age group.
- O Changed estradiol and testosterone level analyses to be change from baseline.
- Made the following changes to Table AMBU.6.6:
 - o Removed as part of the exploratory analyses.
 - o Clarified analyses that will be performed for alternate clinical remission.
 - Updated analysis method for Bristol Stool Scale.
 - Added missing data handling analysis methods for each endpoint variable (NRI, mBOCF, and as observed).
- Updated language in hepatic safety section (Section 6.13.7.1). Added an additional hepatic screening plot.
- Updated hypersensitivity analyses for immediate and nonimmediate events to be in line with adult safety analyses (Section 6.13.7.3).
- Added CDI-2 analysis to suicidal ideation/behavior and depression (Section 6.13.7.7).
- Removed language surrounding per protocol analysis.
- Updated data snapshot and interim analysis language in accordance with the protocol amendments.
- Updated which weeks will be included in GCI diary calculations (Appendix 1).
- Fixed typos and made other minor edits.

4. Study Objectives

4.1. Primary Objective

Table AMBU.4.1. Primary Objective and Endpoints

Objectives	Endpoints
Primary	
To evaluate the pharmacokinetics (PK) of mirikizumab treatment in pediatric patients	Clearance and volume of distribution of mirikizumab

4.2. Secondary Objectives

Table AMBU.4.2 shows the protocol-defined secondary objectives and endpoints of the study. In addition, the analysis of other exploratory endpoints are described in Section 4.3 and Section 6.10.

The estimand (ICH 2019) associated with each endpoint/analysis is documented in the following places:

- The population of interest is described in the protocol inclusion/exclusion criteria and in this document in Section 6.1.1 and Table AMBU.6.4.
- The endpoint/variables may be found in Table AMBU.4.2 and Table AMBU.6.4.
- The handling of intercurrent events and missing data may be found in Section 6.3 and Table AMBU.6.4.
- Population summary measures are described in Section 6.1.3, Table AMBU.6.5, and Table AMBU.6.6.

 Table AMBU.4.2.
 Secondary Objectives and Endpoints

Objectives	Endpoints
Secondary	
To evaluate the effect of treatment	The proportion of patients in modified Mayo score (MMS) clinical
with mirikizumab on achieving	remission at Week 12
clinical remission at Week 12	The proportion of patients in MMS clinical remission at Week 52
and/or Week 52	The proportion of patients in MMS clinical remission at Week 52
	among the MMS clinical remitters at Week 12 (durable clinical
	remission)
	The proportion of patients in MMS clinical remission at Week 52
	among the MMS clinical responders from Week 12
	MMS clinical remission is defined as:
	Stool frequency (SF) subscore = 0 , or SF = 1 , and
	Rectal bleeding (RB) subscore = 0, and
	Endoscopic subscore (ES) = 0 or 1 (excluding friability)
	MMS clinical response is defined below

Objectives	Endpoints
Secondary	
To evaluate the effect of treatment with mirikizumab on achieving clinical response at Week 12 and/or Week 52	The proportion of patients in clinical response at Week 12 The proportion of patients in clinical response at Week 52 The proportion of patients in clinical response at Week 12 who achieve clinical response at Week 52 Clinical response is based on the MMS and is defined as: A decrease in the MMS of ≥2 points and ≥30% decrease from baseline, and A decrease of ≥1 point in the RB subscore from baseline or a RB score of 0 or 1
To evaluate the effect of treatment with mirikizumab on achieving corticosteroid-free remission without surgery among patients in clinical remission at Week 52 and receiving	The proportion of patients who entered the study on corticosteroids and who are in MMS clinical remission at Week 52 without the use of corticosteroids Corticosteroid-free remission without surgery at Week 52 defined as:
corticosteroids at baseline	
To evaluate the effect of treatment with mirikizumab on PUCAI clinical remission at Week 12 and/or Week 52	The proportion of patients in PUCAI clinical remission at Week 12 The proportion of patients in PUCAI clinical remission at Week 52 The proportion of patients in PUCAI clinical remission at Week 12 who achieve clinical remission at Week 52 The proportion of patients in PUCAI clinical response at Week 12 who achieve clinical remission at Week 52 PUCAI clinical remission is defined as a PUCAI score of <10 points PUCAI clinical response is defined below
To evaluate the effect of treatment with mirikizumab on PUCAI clinical response at Week 12 and/or Week 52	The proportion of patients in PUCAI clinical response at Week 12 The proportion of patients in PUCAI clinical response at Week 52 The proportion of patients in PUCAI clinical response at Week 12 who achieve PUCAI clinical response at Week 52 PUCAI clinical response is defined as a reduction in baseline PUCAI score of ≥20 points
To evaluate the effect of treatment with mirikizumab on achieving endoscopic remission at Week 12 and/or Week 52	The proportion of patients in endoscopic remission at Week 12 The proportion of patients in endoscopic remission at Week 52 The proportion of patients in endoscopic remission at Week 12 who maintain endoscopic remission at Week 52 (durable endoscopic remission) Endoscopic remission is defined as: ES = 0 or 1 (excluding friability)
To evaluate the effect of treatment with mirikizumab on achieving ES = 0 at Week 12 or Week 52	The proportion of patients with ES = 0 at Week 12 The proportion of patients with ES = 0 at Week 52
To evaluate the effect of treatment with mirikizumab on symptomatic remission over time	Proportion of patients in symptomatic remission at applicable study visits $ \begin{aligned} & \textbf{Symptomatic remission} \text{ is defined as:} \\ & \textbf{SF} = 0, \text{ or SF} = 1 \text{ with a} \geq 1 \text{-point decrease from baseline and} \\ & \textbf{RB} = 0 \end{aligned} $

Objectives	Endpoints
Secondary	
To evaluate the effect of treatment with mirikizumab on height velocity at Weeks 12, 24, and 52	Observed height velocity by gender and age group will be calculated at baseline, Week 12, Week 24, and Week 52
To evaluate the effect of treatment with mirikizumab on weight throughout the trial	Change from baseline in weight (kg) at all study visits by gender and age group
To evaluate the effect of treatment with mirikizumab on pubertal development throughout the trial in appropriate patient groups	Hormone levels and/or other related clinical measures will be evaluated
To evaluate the effect of treatment with mirikizumab on improving	Change from baseline in 7-day average of Abdominal Pain (in past 24 hours) NRS score at Week 12 and Week 52
patient-reported outcome endpoints at Week 12 and Week 52	The proportion of patients with a NRS pain score ≥3 at baseline who achieve an improvement of ≥30% from baseline in 7-day average abdominal pain NRS score at Week 12 and Week 52
To evaluate histologic-endoscopic mucosal remission following	Proportion of patients with histologic-endoscopic mucosal remission at Week 12
mirikizumab treatment at Week 12 or Week 52	Proportion of patients with histologic-endoscopic mucosal remission at Week 52
	Histologic-endoscopic mucosal remission is defined as achieving both histologic remission and endoscopic remission. Histologic remission is defined in Section 6.10.1.
To evaluate the development of antimirikizumab antibodies and their effect	Proportion of patients who have treatment-emergent anti-drug antibodies (TEADA)
CCI	CCI

Abbreviations: NRS = numeric rating scale; PK = pharmacokinetic; PUCAI = Pediatric Ulcerative Colitis Activity Index.

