9.1.7. Health Outcomes Instruments

Observer-reported outcomes will be used in place of patient-reported outcomes for children less than CCI [REDACTED] for the following scales. The patient's age at entry into the study will determine which scale/instrument is used and this will not change as the patient ages during the study.

Abdominal Pain Numeric Rating Scale: The abdominal pain numeric rating scale (NRS) is a single item that measures the “worst abdominal pain in the past 24 hours” using a Pain NRS ranging from 0 to 5 (8-11 years old) and 0 to 10 (12-17 years old). For children less than 8 years old, caregivers will complete an observer-reported outcome ranging from 0 to 10. Patients or caregivers will be provided with an electronic diary tool during screening to record information daily pertaining to the patient's worst abdominal pain experience.

Urgency Numeric Rating Scale: CCI [REDACTED]

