Prior failured of a JAKg inhibitor	No	Ever, Never
Prior corticosteroid failured	No	Ever, Never
Prior immunomodulator	NI	·
failure ^{d, h}	No	Ever, Never
Baseline UC Therapies		
Baseline corticosteroid useh	No	Yes, No
Baseline prednisone equivalent dose	Yes	None
Budesonide MMX	No	Yes, No
Baseline immunomodulator use ^h	No	Yes, No
Baseline corticosteroid and immunomodulator useh	No	Corticosteroid only, Immunomodulator, Neither, Both
Baseline use of oral aminosalicilatesi	No	Yes, No
Baseline use of methotrexateh	No	Yes, No
Baseline use of thiopurineh	No	Yes, No
Baseline Disease Characteristics		
Duration of UCi	Yes	<1 year, ≥ 1 to <3 years, ≥ 3 year to <7 years, ≥ 7 years
Age at Diagnosis of UCk	Yes	$<6, \ge 6$ to <10 year, ≥ 10 to <17 years
Historical Disease Severity	No	Ever Severe, Never Severe
Baseline Disease Extent	No	Ulcerative proctitis (rectum), Left-sided (descending or sigmoid colon), Extensive (transverse colon), Pancolitis (cecum or ascending colon)
Baseline Fecal Calprotectin	Yes	≤250 μg/g, >250 μg/g
Baseline C-reactive Protein (CRP)	Yes	≤6 mg/L, >6 mg/L
Baseline Modified Mayo Score	Yes	Moderate (4-6), Severe (7-9)
Baseline Total Mayo Score	Yes	Moderate (6-9), Severe (10-12)
Baseline Partial Mayo Score	Yes	None
Baseline Endoscopic Mayo Subcore	No	Possible values of 4-point scale in Table AMBU.6.4
Baseline Stool Frequency Mayo Subscore	No	Possible values of 4-point scale in Table AMBU.6.4
Baseline Rectal Bleeding Mayo Subscore	No	Possible values of 4-point scale in Table AMBU.6.4
Baseline PGA Mayo Subscore	No	Possible values of 4-point scale in Table AMBU.6.4
Baseline PUCAI	No	Severe (65-85), Moderate (35-60), Mild (10-30), None (<10)
CCI		
Baseline Abdominal Pain NRS	Yes	<4,≥4
Baseline Patient's Global Rating of Severity (PGRS)	Yes	None
Baseline Nocturnal Stool	Yes	Yes (≥1), No (0)
Baseline Bristol Stool Scale	No	Not Loose Stool (1 – 3), Loose Stool (4-5)

Abbreviations: ATC = Anatomical Therapeutic Chemical; BMI = body mass index; DOB = date of birth; eCRF = electronic case report form; JAK = Janus kinase; NRS = numeric rating scale; PGA = Physician's Global Assessment; PUCAI = Pediatric Ulcerative Colitis Activity Index; TNF = tumor necrosis factor; UC = ulcerative colitis

- ^a Age in years will be calculated as length of the time interval from the DOB to the informed consent date.
- b Body mass index (BMI) will be calculated as: $BMI(kg/m^2) = Weight(kg)/(Height(m))^2$.

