		Endoscopic Response	A decrease in the ES of ≥1 point compared to baseline.	Missing if ES is missing.
		SF component of clinical remission	SF = 0, or $SF = 1$	Missing if SF is missing.
		RB component of clinical remission	RB = 0	Missing if RB is missing.
		Corticosteroid-free remission at Week 52	Corticosteroid-free remission without surgery at Week 52, defined as: Clinical remission at Week 52, and No corticosteroid use or UC-related surgery for ≥12 weeks prior to Week 52	NRI if any component is missing.
		Loss of Clinical Response	CCI	

Measure	Description	Variable	Derivation / Comment	Definition of Missing
Urgency NRS	CCI	Urgency NRS Score	Calculated by averaging data from all available diary entries of Urgency NRS for a 7 day period as described in Appendix 1.	Missing if fewer than 4 available measurements in the relevant 7 days (see Appendix 1).
Abdominal Pain NRS	The Abdominal Pain NRS is a single patient-reported item that measures the "worst abdominal pain in the past 24 hours" using a 6-point scale ranging from 0 (no pain) to 5 (worst possible pain) for 8-11 years old, and 11-point NRS ranging from 0 (no pain) to 10 (worst possible pain) for children < 8 years old as completed by a caregiver and those 12-17 years old.	Abdominal Pain NRS Score	Calculated by averaging data from all available diary entries of Abdominal Pain NRS for a 7 day period as described in Appendix 1.	Missing if fewer than 4 available measurements in the relevant 7 days.
PGIC	The Patient's Global Impression of Change (PGIC) scale is a patient-rated instrument designed to assess a patients' rating of change in their symptom(s). Responses are graded on a 7-point Likert scale. Patients or caregivers will record their response on the PGIC electronically as source data in the tablet device at appropriate visits.	PGIC Score	Single Item	Single item, missing if missing. No imputation.
PGRS	Patient's Global Rating of Severity (PGRS) is a 1-item patient-rated questionnaire designed to assess the patients' rating of their disease symptom severity over the past	PGRS Score	Calculated by averaging data from all available diary entries of PGRS for a 7 day period as described in Appendix 1.	Missing if fewer than 4 available measurements in the relevant 7 days.

Measure	Description	Variable	Derivation / Comment	Definition of Missing

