	PUCAI clinical response	Proportion for each weight/treatment	mITT	Weeks 12 and 52
		dose group along with the 95%	mITT who achieve PUCAI	Week 52
		2-sided CI with NRI and as observed.	clinical response at Week 12	
	PUCAI CFB	Descriptive statistics and 95% CI for	mITT	Weeks 12, 24, 36, and 52
		mean with mBOCF and as observed.		

		Analysis Method	Population	
Measure	Variable	(Section 6.1.3)	(Section 6.1.1)	Time Point(s)
Height	Height Velocity	Descriptive statistics and 95% CI for	mITT, by gender and age	Weeks 12, 24, and 52
	II : 14 CED	mean.	group	W 1 12 24 152
	Height CFB	Descriptive statistics and 95% CI for mean.	mITT	Weeks 12, 24, and 52
	Height Percentiles CFB	Descriptive statistics and 95% CI for mean.	mITT	Weeks 12, 24, and 52
Weight	Weight CFB	Descriptive statistics and 95% CI for mean.	mITT	At each scheduled visit.
	Weight Percentiles CFB	Descriptive statistics and 95% CI for mean.	mITT	Weeks 12, 24, and 52
Occipital head circumference	Head circumference	Descriptive statistics and 95% CI for mean.	mITT only on those patients less than 3 years at baseline	At all applicable visits (Week 12 + Q12W)
Puberty Development	Testosterone CFB	Descriptive statistics and 95% CI for mean.	mITT – males who are 9 years or older	Weeks 12, 36, and 52
	Estradiol CFB	Descriptive statistics and 95% CI for mean.	mITT – females who are 9 years or older without the date of onset of menstruation.	Weeks 12, 36, and 52
Abdominal Pain NRS	Abdominal Pain NRS score CFB	Descriptive statistics and 95% CI for mean with mBOCF and as observed.	mITT, summarized by age group	Weeks 12 and 52
. The	CCI			Week 12 and 52
CCI			mITT	Weeks 12 and 52
Histopathology	Histologic Remission	Proportion for each weight/treatment dose group along with the 95% 2-sided CI with NRI and as observed.	mITT	Weeks 12 and 52
	Histologic Improvement	Proportion for each weight/treatment dose group along with the 95% 2-sided CI with NRI and as observed.	mITT	Weeks 12 and 52

		Analysis Method	Population	
Measure	Variable	(Section 6.1.3)	(Section 6.1.1)	Time Point(s)
	Histologic-Endoscopic	Proportion for each weight/treatment	mITT	Weeks 12 and 52
	Mucosal Improvement	dose group along with the 95%		
		2-sided CI with NRI and as observed.		
	Histologic-Endoscopic	Proportion for each weight/treatment	mITT	Weeks 12 and 52
	Mucosal Remission	dose group along with the 95%		
		2-sided CI with NRI and as observed.		

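### The abdominal-pain responder endpoint, as visibly defined, applies one raw baseline cut-off (NRS ≥3) to a 0-5 scale and a 0-10 scale, so ages 8-11 enter the denominator on a different criterion.

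*SAP*

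**What the plan says.** The responder endpoint in SAP Section 4.2 (Table AMBU.4.2) is "The proportion of patients with a NRS pain score ≥3 at baseline who achieve an improvement of ≥30% from baseline", assessed at Weeks 12 and 52. The definition has no qualifier for age or instrument.

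Two instruments feed it. SAP Table AMBU.6.4 describes the item as "using a 6-point scale ranging from 0 (no pain) to 5 (worst possible pain) for 8-11 years old", and as an "11-point NRS ranging from 0 (no pain) to 10 (worst possible pain) for children < 8 years old as completed by a caregiver", with the 11-point version also used at ages 12-17. Protocol Section 9.1.7 agrees: the scale is "ranging from 0 to 5 (8-11 years old) and 0 to 10 (12-17 years old", and for children under 8 "caregivers will complete an observer-reported outcome ranging from 0 to 10". The protocol fixes the instrument by age at study entry.

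The derived variable is the raw average: "Calculated by averaging data from all available diary entries of Abdominal Pain NRS for a 7 day period". Neither Table AMBU.6.4 nor SAP Appendix 1 mentions conversion to a common range.

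On reporting, the pain change-from-baseline row of SAP Table AMBU.6.5 is specified as "mITT, summarized by age group", and the SAP Revision History (Section 3) says the same of abdominal pain generally. The row below it is blacked out.

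SAP Table AMBU.6.3 lists "Baseline Abdominal Pain NRS" with both a continuous summary and the categories <4 and ≥4. SAP Section 6.7 has these characteristics summarised by weight/treatment dose group and overall, with no split by age.

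**The concern.** A raw score of 3 sits at a different point on each scale. Read literally, the endpoint admits 8-11 year olds only from 60% of their scale upward and everyone else from 30% upward. Two children reporting pain at the same share of their own scale can therefore be treated differently, one counted and the other left out, because of age alone.

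Two things are at stake. The responder rate for ages 8-11 would describe a differently selected set of children from the other age bands, so a side-by-side reading, or the optional age subgroup analysis in SAP Section 6.14, would confound age with the baseline pain required for entry. In the baseline table, one mean and one <4/≥4 split would combine scores in different units. With about 30 patients planned, moving a few children in or out of a subset can visibly shift a proportion.

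**Working it through.** The plan gives no figure to reproduce for this endpoint: no power, target rate or expected denominator. The check is arithmetic on the stated scales.

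**Inputs.** Responder cut-off 3 (Table AMBU.4.2); baseline category cut-off 4 (Table AMBU.6.3); scale maxima 5 and 10 (Table AMBU.6.4, Protocol 9.1.7).

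**Step 1: cut-off as a share of scale maximum** (cut-off ÷ maximum).

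| Cut-off | Ages 8-11 (0-5) | Ages <8 and 12-17 (0-10) | Ratio |
|---|---|---|---|
| ≥3, responder denominator | 3/5 = 60% | 3/10 = 30% | 2.0 |
| ≥4, baseline category | 4/5 = 80% | 4/10 = 40% | 2.0 |

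**Step 2: sensitivity to how position is measured.** With category midpoints, (3 + 0.5)/6 = 58.3% against (3 + 0.5)/11 = 31.8%, a ratio of 1.83. The gap does not depend on the exact convention.

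**Step 3: who is affected.** Under proportional scales, 30% of the maximum on 0-5 is 0.30 × 5 = 1.5. An 8-11 year old averaging from 1.5 to just under 3 (3.0 to just under 6.0 after doubling) is left out, while a child at the same share of the 0-10 scale is counted.

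**Step 4: possible size, by assumption only.** The documents give no pain distribution. If relative pain U (score ÷ maximum) had the same distribution at all ages, the qualifying share would be P(U ≥ 0.6) on 0-5 and P(U ≥ 0.3) on 0-10:

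| Assumed U | 0-5 scale | 0-10 scale |
|---|---|---|
| Uniform | 40% | 70% |
| Beta(2,2) | 35% | 78% |
| Beta(2,3) | 18% | 65% |
| Beta(3,2) | 53% | 92% |

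**Step 5: the improvement rule.** A 30% reduction is a ratio: (b − f)/b is unchanged if baseline b and follow-up f are both multiplied by 2. The scale problem lies in the entry condition.

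**Step 6: the baseline table.** Take two children each at half of scale maximum, scoring 2.5 on 0-5 and 5 on 0-10. Their raw mean is (2.5 + 5)/2 = 3.75. One falls in <4 and the other in ≥4, although their relative positions are identical.

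**The case against.** **Redaction.** The strongest counter-argument is that the analysis specification cannot be seen. The Revision History says a 30% improvement endpoint for abdominal pain was added to Table AMBU.6.5, and the row under the pain change-from-baseline row is blacked out apart from its time points. It is probably the responder row, and an age-specific population rule would sit naturally there. This stands: the analysis cannot be said to lack such a rule. But SAP Section 4.2 directs the reader to Tables AMBU.4.2 and AMBU.6.4 for endpoint definitions, and the visible pain entries in both carry none.

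**Pooling.** A reader might infer that responder rates on the two scales will be pooled within a dose group. The documents do not support that. The SAP says abdominal pain is summarised by age group, and its bands (2 to <8, 8 to <12, 12 to <18) match the instrument bands. This removes most of the pooling concern for pain results. It does not alter who qualifies within the 8-11 band, and the statement is tied to Table AMBU.6.5, not to the baseline table.

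**Severity wording.** A reader might also say that the rule selects moderate-to-high pain at 8-11 and mild pain elsewhere, or that 8-11 year olds need twice the pain. The documents attach no severity labels to this scale, and a cut-off of 3 on 0-10 admits all higher scores too. The factor of two is a share of scale maximum. The anchors are shared (no pain to worst possible pain), but equal spacing is not established.

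**Comparability and the remedy.** Caregiver and self-ratings differ in any case, so rescaling cannot make the age bands fully comparable. A lower raw cut-off also has a cost: at a baseline of 1.5 a 30% improvement is 0.45 points, or 0.45 × 7 = 3.15 points over seven diary days (four one-step drops). At 3.0 on 0-10 it is 0.9 × 7 = 6.3 (seven one-step drops). Both points stand as limits on the remedy.

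**Weight.** No treatment comparison is planned (SAP Section 6.2), and <4/≥4 defines no endpoint in the visible text. Both points are correct and keep the matter minor.

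**Conclusion.** The point holds as a minor correction. The visible definition uses one raw cut-off on two scales, equal to 60% and 30% of scale maximum (58.3% and 31.8% by midpoints), so the 8-11 denominator is chosen on a different criterion. How many children this moves cannot be known from the documents; the shares in Step 4 are illustrations only.

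The finding on the responder endpoint is conditional on the redacted row of Table AMBU.6.5. If that row holds an age-specific rule, the remaining defect is that Table AMBU.4.2 does not match it. The finding on Table AMBU.6.3 carries no such condition: as written, its continuous summary and its 80%-against-40% split combine the two scales by dose group and overall.

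Reading the ratio as relative pain assumes the scales are proportional. Nothing here reaches the primary PK objective or the sample size, and the endpoint is descriptive.

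**What to change.** Add one derivation rule to SAP Table AMBU.6.4 and refer to it from Tables AMBU.4.2, AMBU.6.3 and AMBU.6.5. Either:

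- put both instruments on a common range before any cut-off is applied, for example 0-5 scores × 2; or
- state scale-specific cut-offs with a reason. Under proportionality these are ≥1.5 for the responder denominator and ≥2 for the baseline category at ages 8-11, with ≥3 and ≥4 kept for the 0-10 scale.

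In Table AMBU.6.3, present baseline pain by instrument or age band, or on the rescaled score. If the redacted row already has an age-specific rule, bring Table AMBU.4.2 into line with it. Leave the ≥30% criterion as it is.

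The cost is a sentence or two and a line of programming. Protocol Section 10.3.1 and SAP Section 6.1 require changes to protocol-described methods to be justified in the study report, or made by amendment if a principal feature changes. The protocol rows that may hold this endpoint are redacted, so the sponsor should check which applies. The downside is the proportionality assumption, including the smaller raw improvement needed at a baseline of 1.5. Caregiver-rated and self-rated scores also remain not strictly comparable, which the report should say.
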